### **13.2.2 Source data verification**

Source data verification ensures accuracy and credibility of the data obtained. During monitoring visits, reported data are reviewed with regard to being accurate, complete, and verifiable from source documents (eg, subject files, recordings from automated instruments, tracings [ECG], x-ray films, laboratory notes). All data reported on the eCRF should be supported by source documents, unless otherwise specified in Section 13.2.1.

## **13.3 Data handling**

### **13.3.1 eCRF completion**

This study will use electronic data capture (EDC); the Investigator is responsible for prompt reporting of accurate, complete, and legible data in the eCRF and in all required reports.

Serious AE reporting will be done using the SAE Form (see [Section 9.2.2](#)) while also entering the event in the appropriate eCRF section. The safety database and the clinical database will be reconciled during the study and discrepancies will be corrected as needed.

The Investigator should maintain a list of personnel authorized to enter data into the eCRF. Access to the EDC will be given after training has been received. A training certificate will be provided and filed.

---

Detailed instructions on the use of the EDC will be provided in the eCRF Completion Guidelines.

Corrections made after the Investigator's review and approval (by means of a password/electronic signature) will be re-approved by the Investigator. Any change or correction to the eCRF after saving must be accompanied by a reason for the change.

### **13.3.2 Database entry and reconciliation**

Case Report Forms/external electronic data will be entered/loaded into a validated electronic database using a clinical data management system. Computerized data cleaning checks will be used in addition to manual review to check for discrepancies and to ensure consistency of the data. This study is performed using EDC: the data are entered into the eCRFs once and are subsequently verified.

An electronic audit trail system will be maintained to track all data changes in the database once the data have been saved initially into the system or electronically loaded. Regular backups of the electronic data will be performed.

### **13.3.3 Subject Screening and Enrollment log/Subject Identification Code list**

The subject's screening and enrollment will be recorded in the Subject Enrollment Log.

The Investigator will keep a Subject Identification Code list. This list remains with the Investigator and is used for unambiguous identification of each subject.

The subject's consent and enrollment in the study must be recorded in the subject's medical record. These data should identify the study and document the dates of the subject's participation.

### **13.4 Termination of the study**

UCB reserves the right to temporarily suspend or prematurely discontinue this study either at a single site, multiple sites, or at all sites at any time for reasons including, but not limited to, safety or ethical issues, inaccurate or incomplete data recording, noncompliance, or unsatisfactory enrollment with respect to quality or quantity.

If the study is prematurely terminated or suspended, UCB (or its representative) will inform the Investigators/institutions and the regulatory authority(ies) of the termination or suspension and the reason(s) for the termination or suspension, in accordance with applicable regulatory requirement(s). The IRB/IEC should also be informed and provided with reason(s) for the termination or suspension by the Sponsor or by the Investigator/institution, as specified by the applicable regulatory requirement(s). In addition, arrangements will be made for the return of all unused IMP and other material in accordance with UCB procedures for the study.

### **13.5 Archiving and data retention**

The Investigator will maintain adequate records for the study, including eCRFs, medical records, laboratory results, Informed Consent documents, drug dispensing and disposition records, safety reports, information regarding participants who discontinued, and other pertinent data.

All essential documents are to be retained by the Investigator until at least 2 years after the last approval of a marketing application in an ICH region and until there are no pending or contemplated marketing applications in an ICH region, or at least 2 years have elapsed since the

formal discontinuation of clinical development of the IMP. These documents should be retained for a longer period, however, if required by the applicable regulatory requirement(s) or by an agreement with UCB (Committee for Proprietary Medicinal Products [CPMP]/ICH/135/95, 2002 [Section 4.9.5]). The Investigator will contact UCB for authorization prior to the destruction of any study records or in the event of accidental loss or destruction of any study records. The Investigator will also notify UCB should he/she relocate or move the study-related files to a location other than that specified in the Sponsor's study master file.

### **13.6 Audit and inspection**

The Investigator will permit study-related audits mandated by UCB, after reasonable notice, and inspections by domestic or foreign regulatory authorities.

The main purposes of an audit or inspection are to confirm that the rights and well-being of the subjects enrolled have been protected, that enrolled subjects (ie, signing consent and undergoing study procedures) are appropriate for the study, and that all data relevant for the evaluation of the IMP have been processed and reported in compliance with the planned arrangements, the protocol, investigational site, and IRB/IEC SOPs, ICH GCP, and applicable regulatory requirements.

The Investigator will provide direct access to all study documents, source records, and source data. If an inspection by a regulatory authority is announced, the Investigator will immediately inform UCB (or designee).

### **13.7 Good Clinical Practices**

Noncompliance with the protocol, ICH-GCP, or local regulatory requirements by the Investigator, institution, institution staff, or designees of the Sponsor will lead to prompt action by UCB to secure compliance. Continued noncompliance may result in the termination of the site's involvement in the study.

## **14 STATISTICS**

A description of statistical methods is presented below and will be described in more detail in the Statistical Analysis Plan (SAP).

### **14.1 Definition of analysis sets**

The Enrolled Set (ES) will consist of all subjects who have given informed consent for PS0018.

The Safety Set (SS) will consist of all subjects who receive at least 1 dose of the study medication in PS0018.

The Full Analysis Set (FAS) will consist of all enrolled subjects who receive at least 1 dose of the study medication and have a valid efficacy measurement for PASI at Baseline of PS0018.

The Pharmacokinetics Per-Protocol Set (PK-PPS) will consist of all enrolled subjects who receive at least 1 dose of the study medication and provide at least 1 quantifiable plasma concentration postdose in PS0018.

### **14.2 Planned safety analyses**

Safety variables will be analyzed for all subjects in the SS.

Adverse events will be coded according to the Medical Dictionary for Regulatory Activities (MedDRA®). Treatment-emergent AEs will be defined as events that have a start date on or following the first administration of study treatment in PS0018 through the final administration of study treatment +140 days (covering the 20-week SFU Period). Treatment-emergent AEs will be categorized to treatment group based on the dose being received at the time of onset of the event. Tables will include columns for bimekizumab 320mg Q4W, bimekizumab 160mg Q4W, and All bimekizumab (ie, either dose of bimekizumab).

Change from Baseline safety variables will be defined relative to the Baseline measurement from PS0016.

#### **14.2.1 Primary safety analysis**

All TEAEs will be summarized descriptively by treatment group, primary system or organ class (SOC), high level term (HLT), and preferred term (PT). This summary will include the exposure adjusted incidence rate (EAIR) with associated 95% confidence interval and the exposure adjusted event rate (EAER).

For EAIR, the numerator will be the total number of subjects experiencing the AE. The denominator will be 100 subject-years; that is, the total summation of individual subject-years at risk up to the first occurrence of the AE for subjects with that AE, and the total subject-years at risk for those subjects not experiencing that AE, divided by 100. Exposure adjusted incidence rates will be presented with a 95% exact confidence interval based upon the Chi-Square distribution (Ulm, 1990).

For EAERs, the numerator will be the number of AEs including repeat occurrences in individual subjects; the denominator will be 100 subject-years. That is, the total summation of individual subject-years at risk divided by 100. No confidence interval will be computed for EAER.

Subject exposure at risk in days will be defined as date of last administration of study medication – date of first administration of study medication +140 days (ie, the duration of the SFU Period). If a subject dies, patient exposure at risk is censored at the date of death. The sum of these exposure days at risk across subjects is converted to years for the EAIR and EAER calculations described above.

#### **14.2.2 Other safety analyses**

Additional tables will summarize TEAEs by intensity and relationship to study medication, TEAEs leading to withdrawal from the study, treatment-emergent SAEs, and deaths.

In order to evaluate if there is any difference in the TEAE profile of subjects who have dose adjustments, additional summaries will be generated and are described further here. With respect to dose adjustments, subjects will be classified into 1 of the following 3 groups:

- Nonadjusters – This group consists of subjects who do not experience a dose adjustment during the study.
- Single adjusters – This group consists of subjects who experience just one dose adjustment during the study. Per the protocol, if just a single adjustment occurs, then that adjustment must be to go from bimekizumab 160mg Q4W to 320mg Q4W.
- Multiple adjusters – This group consists of subjects who experience more than 1 dose adjustment during the study. This means that the subjects in this group dose adjust from

---

bimekizumab 160mg Q4W to 320mg Q4W and then adjust back to 160mg Q4W (with further dose adjustments possible).

Summaries based on these 3 groups will be done by PS0016 randomized treatment group for the TEAE overview, incidence of TEAEs (by SOC, HLT, and PT), and incidence of treatment-emergent SAEs.

Extent of exposure to study medication in PS0018 will be summarized using descriptive statistics. As with the primary summaries of TEAEs, extent of exposure will be presented with columns for bimekizumab 160mg Q4W, bimekizumab 320mg Q4W, and All bimekizumab.

Change from Baseline in laboratory values, ECGs, and vital signs will be presented using descriptive statistics by PS0016 randomized treatment group and overall. As these variables are summarized over time and the initial values can be impacted by the randomized treatment in PS0016, the presentation by PS0016 randomized treatment group is intended to provide perspective on the change in these values starting with the initial PS0016 randomization through the 48-week Open-Label Treatment Period of PS0018. The table presentations will display descriptive statistics for the PS0016 Baseline and the observed and change from PS0016 Baseline results by scheduled visit for PS0018.

### **14.3 Planned PK analyses**

Pharmacokinetic variables will be analyzed for all subjects in the PK-PPS.

Bimekizumab plasma concentrations will be summarized for each treatment at each scheduled visit.

### **14.4 Planned immunological analyses**

Immunological variables will be analyzed for all subjects in the PK-PPS.

Anti-bimekizumab antibody data will be summarized for each treatment at each scheduled visit.

### **14.5 Planned efficacy analyses**

Efficacy variables will be summarized based on the FAS. The summaries described in this section will provide data on maintenance of effect of open-label bimekizumab over 48 weeks. Additionally, it will allow an assessment of the impact of dose adjustments on efficacy results.

Responder efficacy variables (PASI50, PASI75, PASI90, PASI100, IGA score of 0 or 1, and HADS normal scores) will be summarized descriptively using counts and percentages by scheduled visit and PS0016 randomized treatment group and overall. The PASI responder variables are derived relative to the PS0016 Baseline. Missing data will be handled by using nonresponder imputation (NRI), meaning that subjects that discontinue early or who have missing data at a given time point are imputed as though they did not achieve the given response. Supportive summaries will be based on observed case data.

Continuous efficacy variables based on the change from Baseline (PASI, BSA, and HADS) will be summarized using descriptive statistics by scheduled visit and PS0016 randomized treatment group and overall. The table presentations will display descriptive statistics for the PS0016 Baseline and the observed and change from PS0016 Baseline results by scheduled visit for PS0018. Figures for selected variables will also be generated in order to demonstrate the kinetics of response over time. Missing data will be handled by using multiple imputation (MI) via the

Markov-Chain Monte Carlo (MCMC) method. Supportive summaries will be based on observed case data.

In addition to the summaries described above, the impact of dose adjustment on efficacy will be considered. This will be done primarily by summarizing efficacy variables by the 3 adjuster groups as defined in [Section 14.2.2](#). Furthermore, a supportive analysis specifically for single adjusters will be performed in which PASI score will be summarized by visit, where Baseline is recalibrated for each individual subject and defined as the visit where the bimekizumab 320mg Q4W dose is initiated. The visits summarized will be in weeks relative to when the 320mg Q4W dose was started as opposed to the scheduled week of the PS0018 assessment. These summaries will be based on observed data only.

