- 160mg loading dose followed by 80mg at Weeks 3 and 6
- 240mg loading dose followed by 160 mg at Weeks 3 and 6
- 560mg loading dose followed by 320mg at Weeks 3 and 6

The results of this study demonstrated that all doses of bimekizumab were well tolerated and there were no unexpected clinically relevant safety findings.

Infections (mostly nasopharyngitis) were the most commonly reported events in both the active treatment and the placebo group. None of the infections were considered serious or required treatment with antibiotics. Two subjects in the active treatment group experienced 1 local candida infection each (oropharyngitis and vulvovaginitis, respectively) that were nonserious and resolved with topical therapy. There was a reduction in mean neutrophil count in the active treatment group, although this drop was not clinically relevant and a clear relationship with dose or time was not evident. Some increases in liver function tests were reported, but none had a convincing relationship to exposure to study medication. The exploratory analysis showed clinically relevant improvement in activity of psoriatic arthritis and in skin involvement in those subjects with concomitant active psoriatic lesions.

Two additional studies of bimekizumab are ongoing. RA0123 is a Phase 2a, double-blind, randomized, placebo-controlled, multiple dose study to evaluate the safety, PK, pharmacodynamics, and efficacy of multiple doses of bimekizumab administered as add-on therapy to stable certolizumab pegol therapy in subjects with moderate to severe rheumatoid arthritis. UP0031 is a Phase 1 open-label, parallel-group, single-dose study to evaluate the relative bioavailability and tolerability of bimekizumab 160mg sc in healthy subjects.

Additional information on the clinical data for bimekizumab is available in the current version of the Investigator's Brochure (IB).

The current study, PS0018, is a 48-week open-label extension study for eligible subjects who participated in PS0016 (including subjects who relapse at Week 16 through 28 in PS0016), a Phase 2a, randomized, subject-blind, Investigator-blind study in adult subjects with moderate to severe chronic plaque psoriasis. In PS0016, subjects will be randomized 2:1 to receive the following study treatment regimens:

- Treatment arm A: Bimekizumab 320mg administered sc at Baseline and Week 4, followed by placebo administration at Week 16

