## 5.4 Rationale for study design and selection of dose

PS0018 is a 48-week open-label extension study for eligible subjects who participated in PS0016, a Phase 2a, randomized, subject-blind, Investigator-blind study in adult subjects with moderate to severe chronic plaque psoriasis. This study will allow the collection of further data on the long-term safety, tolerability, and efficacy of bimekizumab in this subject population and will provide continued access to bimekizumab.

Bimekizumab will initially be administered at a dose of 160mg Q4W subcutaneously (sc) during the 48 week Open Label Treatment Period. There will be an option to increase the dose to 320mg Q4W at the discretion of the Investigator if the subject's PASI response is  $\geq 50\%$  to  $< 75\%$  reduction from the Baseline of PS0016 at Week 12 or later. If the subject's disease is adequately controlled on the 320mg Q4W dose, they may return to 160mg Q4W at the discretion of the Investigator. The decision to return to 160mg Q4W dosing should be based upon treatment response, tolerability, and Investigator discretion, with the aim to use the dosing regimen that achieves the optimal benefit-risk for each subject. If a subject does not achieve a PASI50 at Week 12 or later then they will be withdrawn from the study.

The rationale for the selection of the 160mg Q4W dose for this study is based on the following:

- The optimal therapeutic dose of bimekizumab will not yet be known at the time subjects begin entering PS0018 from PS0016.
- The 160mg Q4W dose is within the range of doses that have already been explored by iv administration. This dose was selected based on modeling using the currently available data and may be modified, if appropriate, as further data are collected on the optimal dose of bimekizumab.
- The 160mg Q4W starting dose in PS0018 will provide data to evaluate the safety and efficacy of a dose reduction.

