#### **3.5.3 Full Analysis Set**

The Full Analysis Set (FAS) will consist of all enrolled subjects who received at least 1 dose of the study medication and have a valid efficacy measurement for PASI at PS0018 Week 0.

Efficacy variables will be summarized based on the FAS.

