#### **4.10 Examination of subgroups**

Not applicable.

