Furthermore, a supportive analysis specifically for adjusters will be performed in which PASI score will be summarized by visit, where Baseline is recalibrated for each individual subject and defined as the visit where the bimekizumab 320mg Q4W dose is initiated. The visits summarized

will be in weeks relative to when the bimekizumab 320mg Q4W dose was started as opposed to the scheduled week of the PS0018 assessment. These summaries will be based on observed data only.

The PASI50, PASI75, PASI90, and PASI100 responses are based on at least 50%, 75%, 90%, and 100% improvement from Baseline in the PASI score. Thus, the following will apply:

- If the percentage improvement is  $\geq 50\%$  then the subject is a PASI50 responder
- If the percentage improvement is  $\geq 75\%$  then the subject is a PASI75 responder (and is a PASI50 responder also)
- If the percentage improvement is  $\geq 90\%$  then the subject is a PASI90 responder (and is a PASI50 and PASI75 responder also)
- If the percentage improvement is 100% then the subject is a PASI100 responder (and is a PASI50, PASI75 and PASI90 responder also)

The number and percentage of subjects achieving a PASI50, PASI75, PASI90, and PASI100 response will be tabulated by visit and overall and by PS0016 randomized treatment group and by Dose adjustment. The 95% CI for the percentage of responders will be calculated using a Wilson approximation and be included in the tabulation.

In addition, the percentage of responders (including 95% CI) will be plotted at each PS0018 visit for each response variable. Separate plots will be presented for each of PASI50, PASI75, PASI90 and PASI100 with both treatment groups overlaid on the same plot. These plots will be presented by PS0016 randomized treatment and by Dose adjustment separately.

For the purpose of the tabulation the lower and upper 95% confidence limits for the percentage of responders will be truncated at 0 and 100% respectively.

Missing data will be imputed using NRI as described in [Section 4.2.1.1](#). Subjects with missing data will be regarded as non-responders for the PASI50, PASI75, PASI90, and PASI100 variables.

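### The efficacy tables are said to show maintenance of effect, but none is split by response status at PS0018 Week 0, so they do not show how many entrants in response kept it.

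*Protocol*

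**What the plan says.** Protocol 14.5 gives the purpose of the efficacy summaries: "The summaries described in this section will provide data on maintenance of effect of open-label bimekizumab over 48 weeks". Responder variables are to be "summarized descriptively using counts and percentages by scheduled visit and PS0016 randomized treatment group and overall", and "The PASI responder variables are derived relative to the PS0016 Baseline". SAP 8.2.1 adds one further split for PASI: responder counts "will be tabulated by visit and overall and by PS0016 randomized treatment group and by Dose adjustment". SAP 8.2.3 tabulates IGA response by PS0016 arm and overall, and its shift tables also start from PS0016 Baseline. SAP 4.10, headed "Examination of subgroups", is marked not applicable.

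On who enters, Protocol 2.2.1 describes PS0018 as open to eligible PS0016 participants, "including subjects who relapse at Week 16 through 28 in PS0016". Neither document defines relapse or says how many relapsed subjects are expected. The Full Analysis Set (SAP 3.5.3) is limited to dosed subjects who "have a valid efficacy measurement for PASI at PS0018 Week 0", and SAP 3.3 carries Week 0 into the tables as a visit.

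Protocol 5.4 makes a separate statement in the dose rationale: "The 160mg Q4W starting dose in PS0018 will provide data to evaluate the safety and efficacy of a dose reduction".

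**The concern.** Entrants can be of at least two kinds: subjects still in response, and subjects who have lost it. Only the first kind can maintain anything. When both are in one denominator, a subject who gains response cancels a subject who loses it, and the by-visit percentage shows only the net change.

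The planned columns do not undo this. The PS0016 arm may correlate with relapse but does not identify it, since either arm can contain both kinds. Dose adjustment is decided on PASI at Week 12 or later and on investigator discretion, so it is an outcome after entry. For example, a subject who falls from at least 90% improvement to 80% is outside the 50% to below 75% band for a dose increase. That subject can stay a non-adjuster, and no column marks the lost PASI90.

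At stake is a descriptive secondary question. A flat or rising pooled curve could be reported as maintenance when the table does not establish it.

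**Working it through.** The documents contain no calculation to reproduce. The planned number, up to 45, is the planned PS0016 randomization (Protocol 14.7), and 2:1 allocation (Protocol 2.2.1) gives 30 and 15 if all roll over. The check is therefore a count of what a by-visit table can reveal.

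**Notation.** N is subjects in the column, R is responders at Week 0, S is responders at a later visit, and k is Week 0 responders who still respond at that visit. Under non-responder imputation N is the same at every visit.

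**Bounds.** The later responders are k plus those gained from the N − R non-responders at entry, so S − k cannot exceed N − R. Also, k cannot exceed R or S. Hence max(0, R + S − N) ≤ k ≤ min(R, S).

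**Flat overall rate (S = R), N = 45.** The numbers of non-responders at entry are assumptions.

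| Non-responders at entry | R | Table shows at both visits | Smallest k | Retained share k/R |
|---|---|---|---|---|
| 5 (11%) | 40 | 88.9% | 35 | 87.5% to 100% |
| 9 (20%) | 36 | 80.0% | 27 | 75% to 100% |
| 15 (33%) | 30 | 66.7% | 15 | 50% to 100% |
| 23 (51%) | 22 | 48.9% | 0 | 0% to 100% |

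With a flat rate, the losses that can be hidden are at most the number of non-responders at entry.

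**Within PS0016 arm.** In the arm of 30 with 10 non-responders at entry, R = 20, the smallest k is 20 + 20 − 30 = 10, and the range is 50% to 100%. In the arm of 15 with 5, R = 10, the smallest k is 10 + 10 − 15 = 5, and the range is again 50% to 100%.

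**Rising rate.** Suppose 25/45 (55.6%) at Week 0 becomes 33/45 (73.3%). The smallest k is 25 + 33 − 45 = 13, so the table allows 13 to 25 of the 25, or 52% to 100%.

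**What a split would show (assumed counts).** Take 15 non-responders at entry, of whom 12 gain response, while 12 of the 30 responders lose it. The planned table shows 30/45 = 66.7% (Wilson 95% interval 52.1 to 78.6) at both visits. The split shows 18/30 = 60.0% (42.3 to 75.4) among Week 0 responders and 12/15 = 80.0% among the rest.

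**The case against.** The strongest reply is that nothing is lost. SAP 8.2.1 plans individual plots of percentage change in PASI by arm, and listings that flag each PASI response at each visit. SAP 10 adds a plot for each subject with PASI, antibody titer, concentration and dosing. Week 0 is shown, efficacy is descriptive and secondary, and Protocol 14.5 does not define maintenance as response kept by Week 0 responders. If few entrants have lost response, the pooled rate is close to the retained rate. All of this stands and limits the point to the summary tables. It does not remove it: 14.5 attributes maintenance to the summaries, and none of them gives a count or interval for it.

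Four stronger readings are tempting, and the documents do not support them.

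- A reader might infer that the effect is large because Arm A last received active drug at PS0016 Week 4. Residual drug does not give the number of subjects who relapsed, and that number is not stated.
- A reader might infer that every Week 0 non-responder is recapturing a lost response. Some may never have reached that response in PS0016.
- A reader might take a table of Week 0 responders as the evidence on dose reduction that Protocol 5.4 mentions. That description does not fit Arm A responders, who have had no active dose since PS0016 Week 4.
- A reader might want every visit from the first 320mg dose counted as not maintained. Protocol 14.5 speaks of open-label bimekizumab, not of 160mg alone, and Protocol 5.1 allows return to 160mg. Such a rule would be a different estimand and a matter of choice.

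**Conclusion.** The point holds for the summary tables. As planned, the by-visit rates do not identify how many subjects in response at PS0018 entry kept it, whether read overall, by PS0016 arm or by dose adjustment. The size depends on the share of non-responders at entry. At about 11%, a flat rate leaves little room for hidden loss; from about one third, it allows anything from half to all responders to have kept response. Those shares are assumptions. The bounds show what the table permits, not what is likely to happen. The primary safety objective is not affected.

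**What to change.** In SAP 8.2.1 and 8.2.3, add by-visit tables of PASI75, PASI90, PASI100 and IGA response, split by status on the same variable at PS0018 Week 0, for each PS0016 arm and overall. Use non-responder imputation with Wilson intervals and give observed-case versions, as for the existing tables. Include a missing-at-Week-0 category for IGA, because the Full Analysis Set guarantees only PASI. An equivalent shift table from Week 0 would also serve.

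Label the two tables *maintenance among Week 0 responders* and *response among Week 0 non-responders*. Base the maintenance statement in Protocol 14.5 on the first, and keep the pooled tables. State two limitations: the subgroups are small, so intervals will be wide; and splitting on a threshold brings regression to the mean, so some apparent loss and gain will be score variability.

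The cost is a few more tables. No new visit, assessment or subject is needed.
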